#### 11.7 Removal of Subject from Study

We will be following the patients for 3 years. Subjects can be taken off the study treatment and/or study at any time at their own request, or they may be withdrawn at the discretion of the investigator for safety, behavioral or administrative reasons. The reason(s) for discontinuation will be documented and may include:

- 11.7.1 Subject voluntarily withdraws from consent
- 11.7.2 Subject is unable to comply with protocol requirements.
- 11.7.3 Subject demonstrates disease progression to targeted site.
- 11.7.4 Subject experiences toxicity that makes continuation in the protocol unsafe.
- 11.7.5 Development of second malignancy that requires treatment, which would interfere with this study.
- 11.7.6 Treating physician judges continuation on the study would not be in the subject's best interest.
- 11.7.8. Subject becomes pregnant.
- 11.7.9 If a research subject cannot be located to document survival after a period of 2 years, the subject may be considered "lost to follow-up". All attempts to contact the subject during the two years must be documented and approved by the Data Monitoring Committee.

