#### **11.6 Other Response Parameters**

- **11.6.1** Duration of Pain Response: The duration of pain response will be measure from the date that CR or PR was recorded to the date of increase in the VAS at the treated site to a score 2 points higher than the lowest VAS score recorded.
- **11.6.2** Time to Functional Decline: Time from study entry to a Zubrod  $PS \le 3$
- **11.6.3** Overall Survival: The survival time will be measured from the date of accession to the date of death. All patients will be followed for survival. Every effort should be made to document the cause of death.

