#### **13.3 Secondary Endpoints**

Secondary endpoints will be analyzed by the following methods. For overall survival Kaplan-Meier plots and median times will be reported. Time to functional decline will me measured with Kaplan-Meier plots and median times will be reported. Duration of pain response will be measured with Kaplan-Meier plots and median duration of pain response will be reported.

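### Section 11.7.3 permits removal at target-site progression with no provision for continued VAS and no censoring rule, so duration of pain response is open to informative censoring, probably biased long

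*Combined protocol and SAP*

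**What the plan says.** Section 11.7 opens with "We will be following the patients for 3 years". It then lets patients leave study treatment, the study, or both, at their own request, or "they may be withdrawn at the discretion of the investigator for safety, behavioral or administrative reasons". The list of reasons is introduced by "The reason(s) for discontinuation will be documented and may include", and item 11.7.3 is "Subject demonstrates disease progression to targeted site". Item 11.7.4 covers toxicity that makes continuation unsafe.

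What survives removal is limited. Section 11.6.3 states "All patients will be followed for survival". Section 6.11.1 keeps serious events beyond 30 days reportable if they are considered probably related to treatment. No sentence says that VAS, narcotic use or scheduled imaging continues.

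Section 11.6.1 measures duration of pain response from the recorded complete or partial response "to the date of increase in the VAS at the treated site to a score 2 points higher than the lowest VAS score recorded". Progression on imaging is not part of that event. For the analysis, section 13.3 says "Duration of pain response will be measured with Kaplan-Meier plots" and that the median will be reported. It has no rule for progression, removal, death or loss to follow-up.

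**The concern.** Kaplan-Meier assumes that a patient censored at a given time has the same later relapse risk as those still followed. Target-site progression is an unlikely place for that to hold. Section 1.4 offers improved local control as a possible reason for durable pain response; on that reasoning, patients whose treated site progresses are those whose pain is likeliest to return. If they leave at progression and their VAS stops, relapses drop out of the event count and the duration looks longer than it is.

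Two secondary objectives are exposed: duration of pain response (2.2.1), and long-term stability of the treated vertebra (2.2.4), which needs later imaging in these same patients. Because removal is optional, the amount of censoring could also vary between investigators.

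**Working it through.** **1. The plan's own figures.** None is given for duration of pain response. The only design figures are the Simon two-stage designs for one-month response, and they reproduce. Single fraction (5/9, 18/29): early termination 0.746, expected N 14.08, alpha 0.0477, power 0.905. Five fraction (2/6, 7/13): 0.647, 8.47, 0.0431 and 0.905. None depends on follow-up after one month.

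**2. Timing of removal.** Radiation is one fraction, or five fractions at most 7 days apart (6.1.2), so at most 4 × 7 = 28 days. Vertebroplasty falls within one month of starting radiation (8.1). The first scheduled on-study MRI is at 1 month (11.2.5). When progression is found there is normally no protocol treatment left to stop.

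**3. Limits of the bias.** Assume a constant relapse hazard λ and that a share q of relapses, unrelated to their timing, is preceded by progression and removal. With lead time L between removal and relapse, the observed hazard is

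λ(1−q) / [(1−q) + q·exp(−λL)].

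This lies between (1−q)λ and λ. The worst case is removal immediately before relapse, when the median is multiplied by 1/(1−q). An assumed true median of 12 months becomes 12/0.90 = 13.3, 12/0.75 = 16.0, 12/0.50 = 24.0 or 12/0.25 = 48.0 months for q = 0.10, 0.25, 0.50 or 0.75. At the other end, if the VAS rise is recorded at or before the visit that detects progression, the event is counted and the bias is zero at any q.

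**4. On the protocol's visit schedule.** Staff VAS visits fall at months 1, 3, 6 and then every 6 months to 36 (the 2-week visit precedes the assumed start). Assume response from month 1, a true median of 12 months, progression 3 months before relapse in a share q, and departure at the visit that detects it. A relapse found at that same visit counts as an event. Simulation of 200,000 responders gives:

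| q | Estimate at 11 months after response, all progressors removed | Median (months) | Estimate, half removed | Median (months) |
|---|---|---|---|---|
| 0 (VAS continues) | 0.528 | 17 | 0.528 | 17 |
| 0.10 | 0.551 | 17 | 0.539 | 17 |
| 0.25 | 0.589 | 17 | 0.557 | 17 |
| 0.50 | 0.658 | 23 | 0.588 | 17 |
| 0.75 | 0.741 | 23 | 0.622 | 17 |

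The first row agrees with 2^(−11/12) = 0.530 within simulation error. The median reads 17 rather than 12 because relapse is dated at the visit that finds it. With all progressors removed and q from 0.10 to 0.75, an assumed 6-month median moves the 11-month estimate from 0.281 to between 0.304 and 0.543; an assumed 18-month median moves it from 0.654 to between 0.674 and 0.822.

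**5. How many patients.** Sections 1.2 and 1.4 cite 90% and 88% tumour control, so 10-12% local failure. Under the design alternatives:
- Single fraction: 29 × 0.80 = 23.2 responders; 23.2 × 0.10 = 2.3 and 23.2 × 0.12 = 2.8, so 2 to 3 patients.
- Five fraction: 13 × 0.75 = 9.75 responders; 9.75 × 0.10 = 0.98 and 9.75 × 0.12 = 1.17, so about 1 patient.

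If 86% kept long-term relief (1.2), 14% relapse. If every local failure were censored first, q is 10/14 to 12/14, and the curve would read 0.86^(4/14) = 0.96 to 0.86^(2/14) = 0.98. The median would not be reached either way.

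**The case against.** The strongest reply is that the plan does not order any of this. Removal is permitted, not required, and the same section plans three years of follow-up. VAS and MRI share scheduled visits from month 1 (11.2.2, 11.2.5), new pain can itself prompt a whole-spine MRI (11.2.5), and Appendix I leaves spine imaging to the physician. Pain may therefore be recorded first or at the same visit, and the relapse is then counted. The endpoint is a descriptive secondary one, and few patients are likely to be involved.

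Most of that stands, and it rules out several stronger readings:
- A reader might infer that follow-up ends at progression, just before pain returns. The documents make removal optional and give no ordering of progression and relapse.
- A reader might see a contradiction with 11.6.3. There is none: a patient can leave study visits and still be followed for survival.
- A reader might conclude that late toxicity disappears after removal. Section 6.11.1 keeps serious events probably related to treatment reportable; what may be lost is scheduled assessment of the rest.
- A reader might take 11.7.4 as purely an exit from follow-up. Toxicity can arise while fractions or vertebroplasty are still to come.

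The reply does not remove the gap. Progression is a 20% increase in lesion dimension (11.5.2.4), which needs no change in pain. After month 6 the next staff VAS is six months later, so a relapse after removal can go unrecorded.

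**Conclusion.** The concern holds as a risk left open by the plan, not as a planned result. Removal at progression is allowed, VAS is not protected afterwards, and the analysis has no censoring rule. Where removal precedes relapse, censoring at the last VAS is the natural default. It is probably informative, given the link that section 1.4 suggests but does not establish, and the bias would then run towards a longer duration. Long-term stability loses scheduled imaging in the same patients.

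The size cannot be derived from the documents. It runs from zero, when relapse is recorded no later than the visit that detects progression, to a factor 1/(1−q) on the median, which is an upper bound under the exponential assumption. A reader might take those inflated medians as the expected error. The documents do not support that: the medians, q and lead time are all assumed, and on the visit schedule the effect is smaller. The background figures point to 2 to 3 single-fraction patients and about 1 five-fraction patient. The one-month primary endpoint and both Simon designs are unaffected. The change is worth making because the endpoint is named and the remedy is cheap.

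**What to change.** In section 11.7, state that target-site progression and toxicity are recorded with their dates but do not end scheduled VAS, narcotic-use, imaging, adverse-event and survival follow-up to 3 years, unless consent is withdrawn. This concerns data collection only and leaves treatment decisions as they are.

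In section 13.3, state the censoring rule for duration of pain response, covering removal, death and loss to follow-up. Add a sensitivity analysis that counts progression-related removal as the end of pain response.

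The cost is protocol wording and continued data collection in a few patients at visits already scheduled. The small downside is that later VAS scores may reflect further treatment given after progression. That treatment and its date should be recorded so that the analysis can take it into account.

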#### **12.0 DATA COLLECTION**

#### Data should be submitted to:

#### Department of Radiation Oncology Clinical Research Office The University of Texas Southwestern Medical Center Attention: [name], Project Manager [name] [contact]

Patients will be identified only by initials (first middle last) and a unique study ID number assigned to each study participant; if there is no middle initial, a hyphen will be used (first-last). Last names with apostrophes will be identified by the first letter of the last name. Participating sub-sites must remove or black-out identifiers from source documentation that is sent to UTSW.

Study-related data will be stored for 5 years after termination of the study when accrual is no longer taking place and all patients have discontinued follow-up procedures.

#### 12.1 Summary of Data Submission

Item	Recommended Submission Timeline
Demographics	Within 2 weeks of study entry
Eligibility and Entry Characteristics including	Within 2 weeks of study entry
baseline H&P	
Pathology Report	Within 2 weeks of study entry
QOL studies	Within 2 weeks of study entry
SBRT dosimetry information	Within 1 week after completion of SBRT
Follow-up H&P data	After last SBRT treatment, post SBRT
	follow-up at 2 weeks, 1, 3, 6, then every 6
	months to 3 years
QOL forms post treatment	After last SBRT treatment, post SBRT
	follow-up at 2 weeks, 1, 3, 6, then every 6
	months to 3 years
Adverse Event assessment	After last SBRT treatment, post SBRT
	follow-up at 2 weeks, 1, 3, 6, then every 6
	months to 3 years

#### 12.2 Procedures to Maintain Confidentiality

Patient medical information obtained as a result of this study is considered confidential. Patient data will be kept in a locked file in the Clinical Research Office, and all electronic data will be password protected. All reports and communications related to subjects in this study will identify patients only by his/her initials/number. Organizations that may look at and/or copy medical records for research, for quality assurance, and data analysis include: the Institutional Review Board (IRB – a group of people who review the study to protect patient rights), the FDA, the Office for Human Research Protections (OHRP). These agencies may review the research to ensure that it is done safely and correctly. Patient confidentiality will be maintained at all times unless government regulation or applicable law requires disclosure. The investigators are obtaining a Certificate of Confidentiality from the U.S. Department of Health and Human Services (DHHS). This Certificate adds special protections for research information that identifies participants and will help researchers protect subject privacy.

#### **13.0 Statistical Consideration**:

#### 13.1 Single Fraction Treatment Group

#### **Two-Stage Design and Sample Size Justification**

The planned sample size of 29 total eligible subjects is based on Simon two-stage optimal design with an overall significance level of 0.05 and power of 90% (Simon R, 1989). The concept of this design is to permit early stopping when a moderately long sequence of initial failure occurs. The historical response rate to conventional radiation treatments is 50%[27]. This response rate comes from the RTOG 9714 trial which looked at 800 cGy in one fraction vs 3000 cGy in ten fractions. It represents combined complete and partial responses. This trial set the standard of care for

palliation of pain bone metastasis in previously unirradiated patients and thus is used as the historical control for this group. The statistical hypothesis tested is as follows:

H0:  $p \le 50\%$  vs. HA:  $p \ge 80\%$ , where p is one month pain response rate

Rejection of  $H_0$  means that further study of the test treatment should be carried out. Under the above hypotheses, the type I error is the false-positive rate in accepting an ineffective treatment and type II error is the false-negative rate in rejecting a promising treatment.

Stage 1 of the study will include 9 eligible subjects. If at least 6 of 9 eligible subjects respond, an additional 20 subjects will be enrolled into stage 2 of the study. If the total number of patients who respond (among the 29 patients) is 19 or more, the null hypothesis above will be rejected in favor of the alternate hypothesis.

Under the null hypothesis ( $p \le 50\%$ ), the expected sample size of the trial is only 14.

The assumptions and specifications for Simon's two-stage design are detailed in the following table 1

Alpha -----> 0.05

Beta -----> 0.10

Response Probability of Historical Conventional Radiation Treatment (P0) ---> 0.5 Response Probability of Stereotactic Radiation Treatment (P1) ---> 0.8

Optimal Two Stage Design	Optimum Design
First Stage Sample Size (n1)	9
Upper Limit For 1st Stage Rejection of Stereotactic	
Radiation Treatment (r1)	5
Maximum Sample Size (n)	29
Upper Limit for 2nd Stage Rejection of Stereotactic	
Radiation Treatment (r)	18
Expected Sample Size If Response Probability = P0	14.08
Probability of Early Termination at P0	0.75

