The initial complication rate of vertebroplasty in patients with metastatic disease is reported to be approximately 10%[23]. This is significantly higher that observed when the procedure is done for osteoporotic compression fractures (2-5%). This is likely secondary to increased bony destruction in the cancer patient. Reported complications include cement leakage into the spinal canal, neural foramina or paraspinous soft tissue. Notably, most cement leaks are asymptomatic and the long term complication rate is reported to be 1.7%. Cement leakage into the neural foramina can cause a painful radiculopathy which typically improves spontaneously in most patients. Extravasation into the spinal canal can cause spinal cord compression. In some instances surgery to decompress the neural structures was necessary. Extravasation into the epidural venous plexus or inferior vena cava can result in pulmonary embolism[26]. Increased back pain after the procedure has also been reported and is thought to be secondary to local irritation from the PMMA. This typically responds well to a short course of non-steroidal anti-inflammatory medications[25].

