#### **13.2** Five Fraction Treatment Group

#### Two-Stage Design and Sample Size Justification

The planned sample size of 13 total eligible subjects is based on Simon two-stage optimal design with an overall significance level of 0.05 and power of 90% (Simon R, 1989). The concept of this design is to permit early stopping when a moderately long sequence of initial failure occurs. The historical response rate to conventional radiation treatments is 35%[42]. This response rate comes from a subsequent analysis of the Dutch Bone Metastasis Study which looked at 800 cGy in one fraction vs 2400 cGy in multiple fractions. It represents combined complete and partial responses. This analysis details what the response rate to conventional radiation retreatment in the setting of prior irradiation to the treated area and thus is used as the historical control for this group. The statistical hypothesis tested is as follows:

H0:  $p \le 35\%$  vs. HA:  $p \ge 75\%$ , where p is response rate

Rejection of  $H_0$  means that further study of the test treatment should be carried out. Under the above hypotheses, the type I error is the false-positive rate in accepting an ineffective treatment and type II error is the false-negative rate in rejecting a promising treatment.

Stage 1 of the study will include 6 eligible subjects. If at least 3 of 6 eligible subjects respond, additional 7 subjects will be enrolled into stage 2 of the study. If the total number of patients who respond (among the 13 patients) is 8 or more, the null hypothesis above will be rejected in favor of the alternate hypothesis.

Under the null hypothesis ( $p \le 35\%$ ), the expected sample size of the trial is only 9.

The assumptions and specifications for Simon's two-stage design are detailed in the following table 2

Alpha -----> 0.05

Beta -----> 0.10

Response Probability of Historical Conventional Radiation Treatment (P0) ---> 0.35 Response Probability of Stereotactic Radiation Treatment (P1) ---> 0.75

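### Sections 13.1 and 13.2 could close accrual within a stage once the required responders are out of reach: a cheap, low-priority improvement to two correctly specified Simon designs

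*Combined protocol and SAP*

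**What the plan says.** Section 13.1 describes the single-fraction group as "based on Simon two-stage optimal design with an overall significance level of 0.05 and power of 90" percent, with a null response rate of 50% and a target of 80%. The interim rule is "Stage 1 of the study will include 9 eligible subjects. If at least 6 of 9 eligible subjects respond", a further 20 are enrolled. At the end, 19 or more responders among 29 reject the null. Section 13.2 applies the same kind of design to the five-fraction group, with 35% against 75%: "Stage 1 of the study will include 6 eligible subjects. If at least 3 of 6 eligible subjects respond", 7 more are enrolled, and 8 or more responders among 13 reject the null.

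Both sections introduce the design with the same idea: "The concept of this design is to permit early stopping when a moderately long sequence of initial failure occurs". The tables give an early-termination probability under the null of 0.75 and 0.65, and expected sizes of 14.08 and 8.47.

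Section 11.4.1 fixes the primary endpoint at one month. Section 14.0 sets up a committee that sees efficacy data, but gives it no futility rule. The documents give no accrual rate. They contain no rule for closing accrual inside a stage, and no statement that accrual must continue once a group can no longer pass.

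**The concern.** Decisions are written only for full stages. If the first four single-fraction patients all fail to respond, at most 5 of 9 can respond and the required 6 is out of reach. The written rule is nonetheless silent until patient 9. In the five-fraction group, four failures among the first four leave at most 2 of 6 against a required 3, and the rule is silent until patient 6. The same gap exists in stage 2.

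Patients entered after that point cannot alter the primary answer. They would still receive SBRT, as re-irradiation in the five-fraction group, and vertebroplasty where feasible. Section 1.3 says of the latter: "The initial complication rate of vertebroplasty in patients with metastatic disease is reported to be approximately 10" percent. The sponsor also presents the small expected size under the null as a merit of the design, and closing accrual within a stage would make it smaller.

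**Working it through.** **Inputs** (13.1, 13.2 and their tables). n1 and n are the stage 1 and total sizes; r1 and r are the largest responder counts that still fail.

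- Single fraction: n1 = 9, r1 = 5, n = 29, r = 18, p0 = 0.50, p1 = 0.80.
- Five fractions: n1 = 6, r1 = 2, n = 13, r = 7, p0 = 0.35, p1 = 0.75.

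**1. Reproduce the plan.** The probability of early termination is PET = P(X1 ≤ r1), and E[N] = n1 + (1 − PET)(n − n1).

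- Single fraction: PET = (1 + 9 + 36 + 84 + 126 + 126)/512 = 382/512 = 0.746. E[N] = 9 + 0.254 × 20 = 14.08.
- Five fractions: PET = 0.0754 + 0.2437 + 0.3280 = 0.647. E[N] = 6 + 0.353 × 7 = 8.47.
- The rejection probability is the sum over X1 > r1 of P(X1) × P(X2 ≥ r + 1 − X1). It is 0.0477 at p0 and 0.9048 at p1 (single fraction), and 0.0431 and 0.9045 (five fractions).

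The plan's figures reproduce. An exhaustive search confirms that both are the optimal designs for their inputs.

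**2. When failure is certain.** In stage 1 this is at n1 − r1 non-responders, and overall at n − r.

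- Single fraction: 9 − 5 = 4, and 29 − 18 = 11.
- Five fractions: 6 − 2 = 4, and 13 − 7 = 6.

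In stage 1 this can happen as early as patient 4, leaving 5 or 2 patients in the stage. A group that enters stage 2 has at most 3 non-responders. It therefore needs 8 more (single fraction, patient 17 at the earliest, 12 left) or 3 more (five fractions, patient 9, 4 left).

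**3. Effect on the decision.** Once these counts are reached, no later outcome lifts the responder total to the threshold. The decision is the same for every sequence of outcomes, so type I error and power are exactly those in step 1.

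**4. Saving if each result is known before the next patient is treated.** The 4th stage 1 non-responder falls at patient k with probability C(k−1, 3)(1 − p)^4 p^(k−4).

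- Single fraction at p0, k = 4 to 9: 0.0625, 0.1250, 0.1562, 0.1562, 0.1367, 0.1094. Patients saved are 5, 4, 3, 2, 1, 0, so the mean saving is 0.3125 + 0.5000 + 0.4686 + 0.3124 + 0.1367 = 1.73. E[N] becomes 14.08 − 1.73 = 12.35.
- Five fractions at p0, k = 4 to 6: 0.1785, 0.2499, 0.2187. The mean saving is 2 × 0.1785 + 0.2499 = 0.61. E[N] becomes 8.47 − 0.61 = 7.86.

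An exact recursion that also closes stage 2 gives 11.38 and 7.15, total savings of 2.70 and 1.32. At p1 the change is 27.29 to 27.15 and 12.74 to 12.65.

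**5. Allowing for the one-month lag.** The accrual rate is not given, so I assume L further patients have been treated when the deciding result arrives, and that accrual pauses at the end of stage 1. A group settled at patient k then treats min(k + L, end of stage). Exact results at p0:

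| L | Single: E[N] | Single: P(at least one spared) | Five: E[N] | Five: P(at least one spared) |
|---|---|---|---|---|
| No rule | 14.08 | – | 8.47 | – |
| 0 | 11.38 | 83% | 7.15 | 70% |
| 1 | 12.21 | 67% | 7.85 | 40% |
| 2 | 12.88 | 50% | 8.26 | 15% |
| 3 | 13.38 | 32% | 8.41 | 6% |

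The single-fraction savings for L = 1, 2, 3 are 1.9, 1.2 and 0.7 patients; the five-fraction savings are 0.6, 0.2 and 0.1. With two pending in the five-fraction group, closing stage 1 early spares nobody (4 + 2 = 6), and what is left of the saving comes from stage 2.

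**The case against.** Three stronger readings are tempting, and the documents support none of them.

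- *The rule contradicts the stated concept.* A reader might infer this from the sentence about initial failures. That sentence speaks of permitting a stop after a moderately long run. The stage 1 look does so, with probability 0.75 and 0.65 under the null. It does not promise a stop at the first patient who makes success impossible.
- *The plan requires treating patients after the result is settled.* This is an inference from the stage 1 size and from silence. No section orders accrual to continue, and the committee in 14.0 could see a settled result.
- *The design is wrong.* A Simon design looks at n1 and n, and this one is applied as named, with every stated figure reproduced. Curtailment is an addition to it.

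The remaining objections concern size. The reductions of 19% (2.70/14.08) and 16% (1.32/8.47) are zero-lag upper bounds, and in the five-fraction group little is left once two patients are pending. The burden should not be exaggerated either. Section 1.3 adds that most cement leaks are asymptomatic and gives a long-term complication rate of 1.7%, and some patients omit vertebroplasty. Full stages also supply data on toxicity, duration of response, functional decline and survival. All of this stands, and it sets the priority.

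Closing on a single recorded non-response also makes each classification decisive as it arrives, while 2.1 and 11.4.2 differ on the complete-response score (0–1 against 0) and on how plainly partial relief carries the narcotic condition. This is a reason to count only confirmed non-responses. It is not a reason to leave the gap.

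**Conclusion.** This is a cheap improvement of low priority, and it corrects no error. Sections 13.1 and 13.2 lack a rule for closing accrual within a stage once the group cannot pass. Adding one leaves all decisions and error rates unchanged. At p0 it saves on average at most 2.7 patients (single fraction) and 1.3 (five fractions). With one to three patients pending, the saving is about 1.9 to 0.7 and 0.6 to 0.1. At p1 it is under 0.2 patients, so a promising treatment gives up almost nothing.

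The certainty counts and the unchanged error rates follow from the plan's thresholds alone. The size of the saving rests on independent patients with a common response rate, on an assumed number pending, and on a pause in accrual between stages.

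**What to change.** Add to 13.1:

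> Accrual to this group closes for futility once a 4th confirmed one-month non-responder is recorded among the first 9 eligible subjects, or an 11th among the 29.

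Add to 13.2:

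> Accrual to this group closes for futility once a 4th confirmed one-month non-responder is recorded among the first 6 eligible subjects, or a 6th among the 13.

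Keep all pass thresholds (6 of 9, 19 of 29, 3 of 6, 8 of 13). Keep 14.08 and 8.47 as the stated expected sizes under H0, and add that curtailment can lower them to no less than 11.38 and 7.15, depending on how many patients are pending. Reconcile the response definitions in 2.1 and 11.4.2 so that a confirmed non-responder has one meaning.

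The cost is two sentences, plus sending each one-month result to the coordinating office as it arrives. A group that has already failed would contribute slightly fewer patients to toxicity and secondary endpoints, within the average savings given above.
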